9.7 Follow up Visits – Stage B

(Days 210 [±7 day], 240 [±7 Days], 270 [±7 Days], 300 [±7 Days], 330 [±7 Days], and 360 [±7 Days])

- Clinical assessments
 - o Brief physical exam, including the injection site for infections or inflammation
 - Measure vital signs (temperature, heart rate, blood pressure, and respiratory rate)
- Efficacy assessments
 - Record BPI scores (Appendix 2)
 - Record KOOS scores (Appendix 3)
 - O Record participant's response to the question: "Considering all the ways the OA in your knee affects you, how are you doing today?" on a scale of 1 to 5, 1 being very good (asymptomatic and no limitation of normal activities) to 5, very poor (very severe, intolerable symptoms and inability to carry out normal activities)
 - Record changes in drug regimens or pain therapy
 - Obtain serum for analysis of anti-IL-10 antibodies (Day 360)
 - Obtain serum for pregnancy test (Day 360)
- Assess, identify, and record any AEs since last visit
- At participant's option, administer a second injection to the Index Knee. The second injection will be XT-150 active drug, randomly assigned to be either 150 μg or 450 μg. Record reason provided by the participant for requesting the second injection.
- Record any changes in concomitant medications including prescription, OTC, and herbal medications.

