Scheduled Event	Day -30 to Baseline	Day 0	7 (±1)	30 (±2)	60 (±7)	90 (±7)	120 (±7)	150 (±7)	180 (± 7)
Informed consent b	X								
Complete medical history and physical examination ^c	X								
Kellgren-Lawrence grading (may require new radiograph)	X								
Quantitative Sensory Testing	X								
Patient training on pain reporting	X	X	X	X	X	X	X	X	X
Record prior medications d	X								
Efficacy Assessments									
KOOS/WOMAC e	X	X	X	X	X	X	X	X	X
BPI		X	X	X	X	X	X	X	X
Patient response to OA questionf		X	X	X	X	X	X	X	X
		X	X	X	X	X	X	X	X
		X		X	X		X		X
		X	X	X	X	X	X	X	X
Clinical Assessments									
Brief physical examination		X	X	X	X	X	X	X	X
Record height and weight, calculate BMI	X								X
Vital signs	X	X	X	X	X	X	X	X	X
Clinical exam of the treated joints	X	X	X	X	X	X	X	X	X
Record AEs		X	X	X	X	X	X	X	X
Record SAEs		X	X	X	X	X	X	X	X
Record concomitant medications		X	X	X	X	X	X	X	X
Laboratory Assessments									
HIV, Hepatitis B and C	X								
Serum pregnancy ⁱ	X								
PT/INR, PTT	X				X				
CBC with differential and platelets count	X				X				

Sahadulad France	Screen	Baselinea	Follow up Visit Day ^l						
Scheduled Event	Day -30 to Baseline	Day 0	7 (±1)	30 (±2)	60 (±7)	90 (±7)	120 (±7)	150 (±7)	180 (± 7)
Serum chemistry	X				X				
Serum for anti-IL-10 antibody assessments		X	X	X	X				X
Study Drug Administration									
Enroll participant ^j		X							
Administer study drug ^k		X							X

AE = adverse event; BMI = body mass index; BPI = Brief Pain Inventory of Intensity and Interference; CBC = complete blood count; INR = international normalized ratio; ; IL-10 = interleukin 10; KOOS=Knee injury and Osteoarthritis Outcome Score (includes WOMAC measures); PT = prothrombin time; PTT = partial thromboplast in time; SAE = serious adverse event

[figure not shown]
Footnotes to Table 1

- a. Baseline assessments are performed within 1 day before drug injection.
- b. Informed consent must be obtained before initiating any study procedures.
- c. Obtain complete, relevant, medical, and surgical history (including currently active conditions and inactive pain conditions diagnosed) at the Screening visit. Update medical and surgical and pain treatment history at the baseline visit. The physical examination includes the injection site for infections or reactions.
- d. Record prior medications, including prescription and nonprescription medications and herbal supplements. Update prior medications at the baseline visit.
- e. WOMAC Total Score at Screening > 8

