- f. Participant assessment will be recorded in response to the question: "Considering all the ways the OA in your knee affects you, how are you doing today?" on a scale of 1 to 5, 5 being worst
- i. Women of child-bearing potential
- Verify that the participant meets all study inclusion and exclusion criteria before enrollment as close to study drug dosing as
 possible.
- k. Participant will receive a single, 1-mL dose of study drug into the intra-articular space of the knee on Day 0. Participant may elect a second injection on Day 180 (enters Stage B) after efficacy assessments have been recorded.
- A telephone call documenting safety and efficacy assessments may be used for participants unable to physically attend follow
 up visits due to COVID-19 infection or corona virus exposure concerns

Table 2. Schedule of Assessments and Procedures - Stage B

Scheduled Event	Follow up Visit Day ^d							
	210	240	270	300	330	360		
	(±7)	(±7)	(±7)	(±7)	(±7)	(±7)		
KOOS/WOMAC	X	X	X	X	X	X		
BPI	X	X	X	X	X	X		
Patient response to OA question	X	X	X	X	X	X		
	X	X	X	X	X	X		
						X		
Brief physical examination	X	X	X	X	X	X		
Record height and weight, calculate BMI						X		
Vital signs	X	X	X	X	X	X		
Clinical exam of the treated joints	X	X	X	X	X	X		
Record AEs	X	X	X	X	X	X		
Record SAEs	X	X	X	X	X	X		
	X	X	X	X	X	X		
Record concomitant medications	X	X	X	X	X	X		
Serum for anti-IL-10 antibody assessments						X		
Serum pregnancy test ^b						X		
Administer study drug ^c	X	X	X	X	X			

Footnotes to Table 2

- b. Women of child-bearing potential
 c. Participants may elect for one (1) XT-150 IA injection into the Index Knee at any point during Stage B up to Day 330, inclusive. The XT-150 dose (150 μg or 450 μg) will be randomly assigned.
- d. A telephone call documenting safety and efficacy assessments may be used for participants unable to physically attend follow up visits due to COVID19 infection or corona virus exposure concerns

$\mathbf{T}A$	BLE OF CONTENTS	
PF	OTOCOL SYNOPSIS	3
TA	BLE OF CONTENTS	10
	ST OF ACRONYMS, ABBREVIATIONS AND DEFINITIONS (
	RMS	
	CKGROUND AND RATIONALE	
4.1	XT-150	
4.2		
4.3	1	
4.4		

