6.5 Method of Treatment Assignment and Blinding

After informed consent has been obtained, participants will be screened for study eligibility before enrollment.

In Stage A, participants will be randomly enrolled into one of 3 groups, two XT-150 treatment groups (150 μg or 450 μg) or placebo.

At any time in Stage B up to Day 330, inclusive, participants can elect for a single injection to the knee dosed in Stage A (Index Knee). The second injection dose will be randomized to be either 150 μ g or 450 μ g XT-150. There will be no placebo comparator in Stage B.

Instructions for study drug preparation and dosing are given in Section 8.0.

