9.1 Screening

Unless otherwise indicated, screening assessments should be performed within 30 days of enrollment.

- Obtain signed informed consent prior to initiating any study-related assessments or procedures
- Obtain a complete medical history and risk factors (e.g., active malignancy, diabetes mellitus, immunosuppression, transplant recipient, trauma, dialysis) and Intensive Care Unit admission and discharge (if applicable)
- Kellgren-Lawrence grading (obtain a new radiograph if not done in 6 months prior to Screening (See Appendix 5: Kellgren-Lawrence Grading)
- Choice of Index Knee
 - o Meets radiographic criteria: Kellgren-Lawrence grade 2 or 3

- o WOMAC Pain Subscore ≥ 8
- o If bilateral OA and both knees meet the first 2 criteria, the participant and investigator will jointly identify which knee will receive study drug
- o Record Left or Right knee as the Index Knee
- Obtain history of all pain medications and all other medications (prescription and over-the-counter [OTC]) and supplements)
- Conduct FAST assessment
- Participant training on accurate pain reporting
- Clinical assessments
 - Conduct complete physical examination, including height and weight (calculate body mass index [BMI])
 - o Measure vital signs (temperature and the site collected [oral, rectal, temporal, or tympanic], heart rate, blood pressure, and respiratory rate)
 - o Verify WOMAC Pain Subscore ≥ 8 attributable to the Index Knee.
- Laboratory assessments
 - Obtain blood samples for:
 - Hematology tests (complete blood count [CBC] with differential and platelets count),
 - coagulation laboratory tests (prothrombin time [PT] / international normalized ratio [INR] and either partial thromboplastin time [PTT] or activated partial thromboplastin time [aPTT]),
 - HIV, Hepatitis B and C
 - Serum pregnancy test for women of child-bearing potential
 - Serum chemistry tests (Appendix 1)
- Confirm participant qualification by inclusion/exclusion criteria

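### No pregnancy test is scheduled before the optional second injection, so the last one is nominally 180 to 360 days old at re-dosing

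*Protocol*

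**What the plan says.** **Pregnancy tests.** Section 9.1 lists a "Serum pregnancy test for women of child-bearing potential". In Table 1 the row "Serum pregnancy" is marked at Screening only, not at Day 0 or Day 180. In Table 2 the row "Serum pregnancy test ^b" is marked at Day 360 only. Section 9.7 agrees: "Obtain serum for pregnancy test (Day 360". Sections 9.5 and 9.6 list no pregnancy test.

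**Second injection.** Table 1 marks dosing at Day 0 and Day 180. In Table 2 the row "Administer study drug ^c" is marked at Days 210 to 330, and footnote c allows the injection "at any point during Stage B up to Day 330, inclusive". The dose is 150 µg or 450 µg, assigned at random. Section 6.5 adds: "There will be no placebo comparator in Stage B".

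**Pregnancy risk.** Section 10.10 says that XT-150 has not been assessed in pregnancy, and it relies on an agreement to use contraception throughout the study. Pregnancy itself is not one of the 19 exclusion criteria in Section 7.2.

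**The concern.** The protocol tests before the first injection, when one participant in three receives placebo. It does not test again before the second injection, when every recipient gets active drug. For participants randomised to placebo in Stage A (two of the six treatment sequences in SAP Section 4.4), the second injection is also their first exposure to XT-150.

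A site that follows the schedule exactly can therefore give active XT-150 to a woman with an unrecognised pregnancy, after an interval of half a year to a year since anyone last checked. What is at stake is an avoidable fetal exposure to a product with no pregnancy data. It is not a matter of bias or power.

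**Working it through.** The documents state no figure for the age of the test, so there is none to reproduce. The check is arithmetic on the schedule.

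**Inputs**
- Screening test: between Day -30 and Day 0 (Table 1; Section 9.1).
- First injection: Day 0.
- Second injection: Day 180 (Table 1; Section 9.6) to Day 330 inclusive (Table 2, footnote c; Section 6.5).
- Next test: Day 360 (Table 2; Section 9.7).

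**Formulas**
- Age of last test = injection day − day of Screening test.
- Delay to next test = 360 − injection day.

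**First injection:** 0 − 0 = 0 days to 0 − (−30) = 30 days.

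**Second injection,** at nominal visit days:

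| Injection day | Age of last test (days) | Day 360 test follows by (days) |
|---|---|---|
| 180 | 180 − 0 = 180 to 180 + 30 = 210 | 180 |
| 210 | 210 to 240 | 150 |
| 240 | 240 to 270 | 120 |
| 270 | 270 to 300 | 90 |
| 300 | 300 to 330 | 60 |
| 330 | 330 − 0 = 330 to 330 + 30 = 360 | 30 |

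Overall, the last test is nominally 180 to 360 days old at the second injection, and the next test follows 30 to 180 days after it. Footnote c does not tie the injection to a scheduled visit, so the rows are examples within a continuous range.

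The lower end of each age range is slightly optimistic. Appendix 4 says that the result of the pain-reporting test takes 48 to 72 hours. If the pregnancy sample is drawn at that same screening visit, the lower ends rise by about 2 to 3 days.

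**Would anything else reveal a pregnancy before re-dosing?**
- *Contraception (Section 7.1, item 8; Section 10.10):* lowers the risk but detects nothing. The protocol tests at Screening despite it, so it does not treat contraception as a substitute for a test.
- *Exclusion 19 (Section 7.2):* leaves room for the investigator's judgment, but it is an entry criterion.
- *Medical Monitor note (Section 7.4.2):* applies when a participant's situation is known to have changed in the 24 hours before injection.
- *Visit procedures (Sections 9.6 and 9.7):* brief examination, vital signs, adverse events and concomitant medications. None is designed to find an early pregnancy.

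**The case against.** The strongest reply is that the risk is small. Entry starts at age 45. Contraception is required of men and women for the whole study. Section 4.4.3.1 describes a plasmid designed not to integrate, and Section 10.2 expects systemic IL-10 more than 1000-fold below that seen with protein dosing. The documents give neither a count of women of child-bearing potential nor a contraceptive failure rate, so the risk cannot be sized. All of this stands and limits the weight of the point, but none of it supplies a test before re-dosing.

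Redaction is a fair second reply, since both tables have unlabelled rows and Sections 9.4 and 9.6 have gaps. The pregnancy rows, however, are legible in both tables and agree with the visit lists.

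Two stronger readings are tempting and should not be drawn.

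- *That the second injection lacks a needed eligibility re-check.* For the first dose, the Table 1 footnote says: "Verify that the participant meets all study inclusion and exclusion criteria before enrollment as close to study drug dosing". Sections 9.6 and 9.7 show no counterpart. But a repeat of the criteria would not itself reveal a pregnancy, because pregnancy is not a listed exclusion. Section 8.7.1 lists treatments barred before study drug without limiting the bar to the first dose, and medications, adverse events and examination are reviewed at every visit. The text where such a step would appear is partly blacked out. The documents do not establish a separate harm here.
- *That the gap can be counted as a fixed number of untested visits, or bounded to the day with the ±7-day windows.* Footnote c allows dosing at any point, and Section 9.0 allows visits outside the windows after discussion with the Medical Monitor. Only the nominal range is supported.

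**Conclusion.** The point holds as a narrow participant-safety gap. No pregnancy test is scheduled between Screening and Day 360, while an always-active injection is allowed from Day 180 to Day 330. The last test is nominally 180 to 360 days old at re-dosing, compared with 0 to 30 days at the first injection.

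This rests on the legible schedule rows and on nominal study days. The number of women affected is not given; that it is small is an inference from the age limit. A reader might also infer that pregnancies were in fact exposed, or that the trial's results are affected. The documents report no such exposure, and no efficacy or safety estimate depends on the test.

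**What to change.** In Table 1 (Day 180), Table 2 (dosing row and footnote c) and Sections 9.6 and 9.7, require a negative urine or serum pregnancy test in women of child-bearing potential on the day of the second injection, whenever that falls, and before dosing. State outright that a positive test bars the injection, because the exclusion list does not do so. The last test would then be about 0 days old at re-dosing.

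The cost is one simple test per re-dosed woman of child-bearing potential. Blood is already drawn at Day 180 for anti-IL-10 antibodies. No blood draw is legibly scheduled at Days 210 to 330, so a urine test with a same-visit result is the easier choice. During the trial this would have been a short amendment. The SAP addendum was written after database lock and unblinding, so the change now belongs in any later protocol with repeat dosing.

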10.0 ASSESSMENT OF SAFETY

10.1 Safety Parameters

Safety will be assessed through the evaluation of AEs, vital signs, and serum laboratory data according to the Schedules of Assessments and Procedures presented in Table 1 and Table 2 and assessment of anti-IL-10 antibodies is described in Section 12.0.

10.2 Adverse Events of Noted Interest in IL-10 Protein Trials

Safety will include the following reported IL-10 protein-associated toxicities as defined by Common Terminology Criteria for Adverse Events (CTCAE) criteria (version 5.0). Systemic levels of XT-150 produced IL-10 protein is expected to be more than 1000-fold lower than when given as a protein solution (Huhn 1997); and XT-150 will be predominately localized to the knee space.

- Grade 1 (unexplained) fever 38.6°C to 39°C
- Grade 2 allergic, cytokine release, or infusion-related reactions Therapy or infusion interruption indicated but responds promptly to symptomatic treatment (e.g., antihistamines, NSAIDS, narcotics, IV fluids); prophylactic medications indicated for ≤24 hours
- Grade 2 injection site reaction Pain; lipodystrophy; edema; phlebitis
- Grade 2 neutropenia <1500 to $1000/\text{mm}^3$; <1.5 to $1.0 \times 10^9/\text{L}$

10.3 Adverse Events

Medical history will be collected for all participants at the time of informed consent. After consent, all AE's will be collected. The Investigator will assess all AEs and SAEs and will record the following information on the appropriate CRF page:

- Date of onset
- Date of resolution or stabilization
- Severity
- Relationship to study drug
- Action taken with study medication

Medically indicated laboratory tests (emergency or unscheduled tests) should be conducted at the local laboratory. The Investigator should employ best medical judgment in determining how to manage AEs and SAEs. Any questions regarding AE or SAE management should be directed to the Medical Monitor.

10.4 Adverse Event Reporting

The Sponsor has obligations for expedited reporting of SAEs meeting specific criteria to worldwide regulatory authorities. Therefore, the Sponsor must be notified immediately regarding any SAE that occurs after informed consent.

All SAEs must be reported to the Medical Monitor by phone or email within 24 hours of the investigational site's knowledge of the event.

All SAEs and discontinuations due to AEs will be reported to the IRB/HREC.

The study site will also transmit a Serious Adverse Event Report (SAER) to the site study monitor and sponsor by facsimile or email within 24 hours. Contact details will be provided to all sites. An optional initial report can be made via telephone, but a completed SAER must still be faxed or emailed within 24 hours of the site's knowledge of the event. The study sites will be provided with SAER forms wherein the following information is requested.

- Participant identification, Investigator name, and site number
- SAE information: event term, onset date, severity, and causal relationship

- The outcomes attributable to the event (i.e., death, a life-threatening AE, inpatient hospitalization, prolongation of existing hospitalization, a persistent or significant disability or incapacity, or other important medical event[s])
- A summary of relevant test results, pertinent laboratory data, and any other relevant medical history
- The first and last dates of study drug administration. NOTE: as this is a double-blind study, SAERs should not indicate specific study drug assignments
- Indicate if the study drug was discontinued or the study drug administration schedule modified
- Supplemental information may include the following hospital records: laboratory results, radiology reports, progress notes, admission and emergency room notes, holding and observation notes, discharge summaries, autopsy reports, and death certificates

In addition, relevant CRF pages should be appended to communicate relevant study drug and participant outcome information. The SAER should be faxed or emailed within 24 hours with as much of the above information as available at the time. The following minimum information is required for reporting an SAE: participant identification, reporting source, and an event or outcome. Supplemental information may be transmitted using a follow-up report and should not delay the initial report. The Sponsor may contact the investigational site to solicit additional information or follow up on the event.

The Investigator must take all therapeutic measures necessary for resolution of the SAE. Any medications or procedures necessary for treatment of the SAE must be recorded on the appropriate pages of the participant's CRF.

10.5 Definitions

10.5.1 Adverse Event

An AE means any untoward medical occurrence associated with the use of a drug in humans, whether or not considered drug related. An AE (also referred to as an adverse experience) can be any unfavorable and unintended sign (e.g., a clinically significant abnormal laboratory finding), symptom, or disease temporally associated with the use of a drug, and does not imply any judgment about causality. An AE can arise with any use of the drug and with any route of administration, formulation, or dose, including an overdose.

Osteoarthritis-related events should not be considered or recorded as AEs unless the event fits the definition for an SAE (Section 10.5.4), in which case the SAE form must be submitted for safety reporting in the appropriate timeframe and entered as an AE into the CRF.

Laboratory abnormalities should not be recorded as AEs or SAEs unless they are associated with clinical signs or symptoms, or require medical intervention. However, each laboratory abnormality (e.g., clinically significant changes detected on hematology, or lab chemistries) independent from any underlying medical condition that requires

medical or surgical intervention, or that leads to interruption of study drug infusion or discontinuation, must be recorded as an AE, or SAE if applicable. If the laboratory abnormality is part of a clinical condition or syndrome, it should be recorded as the syndrome or diagnosis rather than as the individual laboratory abnormality. In addition, laboratory abnormalities or other abnormal test assessments that are associated with signs or symptoms must be recorded as AEs or SAEs if they meet the definition of an AE (or SAE) as described above or in Section 10.5.4.

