1.0 PROTOCOL SYNOPSIS

Sponsor: Xalud Therapeutics, Inc./Xalud Therapeutics Australia Pty LTD

Study Number: Protocol XT-150-2-0204

Product Name: XT-150

Protocol Title: A Double-Blind, Placebo-Controlled Assessment of the Tolerability and Efficacy of

XT-150 for the Treatment of Moderate to Severe Pain Due to Osteoarthritis of the Knee

Planned Study Centers: 5 (US and Australia)

Phase of Development: 2

Objectives

Primary: To confirm the safety and tolerability of intra-articularly-injected XT-150

Secondary: To establish analgesic efficacy of intra-articularly-injected XT-150

Study Design

This is a Phase 2 safety and efficacy study of XT-150 in adult participants experiencing moderate to severe pain due to osteoarthritis of the knee.

Participants will provide informed consent and meet all study eligibility criteria before any study procedures are initiated. Baseline confirmation of study eligibility will be completed the day before or day of study drug administration. The Index Knee for study drug injection will be the OA-affected joint identified by Kellgren-Lawrence grade of 2 or 3; and WOMAC Pain Subscale \geq 8 on a scale of 20.

Study drug will be administered by intra-articular (IA) injection into the joint space of the Index Knee.

About 270 participants will be randomly enrolled into 1 of 3 treatment groups (approximately 90 participants/ group). Treatment Groups:

- A. Placebo (1 mL)
- B. 150 μg XT-150 (1 mL)
- C. 450 µg XT-150 (1 mL)

Participants will undergo the study in 2 stages, A and B:

- D. Placebo-controlled for 6 months
- E. Continued follow up for 6 months with the option of randomly receiving a single 150 μg or 450 μg injection as the second injection to the Index Knee (knee dosed in Stage A).

Safety parameters and efficacy endpoints for each participant will be evaluated monthly for about 1 year from the first XT-150 dose (Stage A, Day 0)

The Schedule of Assessments and Procedures is presented in Table 1 (Stage A) and Table 2 (Stage B). Day 0 is defined as the day of study drug administration. Subsequent study days are defined by the number of consecutive calendar days after drug administration.

Number of Participants and Treatment Groups:

About 270 participants will be enrolled in one of 3 treatment groups (90 participants/group) and evaluated.

Inclusion Criteria

Participants are required to meet ALL of the following inclusion criteria:

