4.0 BACKGROUND AND RATIONALE

4.1 XT-150

Complete and current information on XT-150 can be found in the Investigator's Brochure (IB) version 7, 24 May 2019.

XT-150 is a new treatment for chronic pain from pathogenic inflammation. It is a plasmid designed to transiently express a variant of the anti-inflammatory cytokine, interleukin-10 (IL-10).

The mechanism of action of XT-150 is through a reduction in inflammation. XT-150 returns target tissues to normal function by induction and release of a single-amino acid variant human IL-10 (a human anti-inflammatory cytokine, IL-10var), that acts to modulate inflammation through multiple pathways: Suppressing pro-inflammatory cytokine production and release, down-regulating cytokine receptors and up-regulating antagonists; and inhibiting hydrogen peroxide and nitric oxide production (Moore 2001; Sawada 2001).

When XT-150 is administered by injection at the site of chronic inflammation, low levels of human IL-10var protein are produced over the following weeks, which reduces the pain associated with joint inflammation.

Additionally, the targeted delivery of XT-150 directly to the joint knee space restricts the potential for systemic AEs.

XT-150 presents a treatment opportunity for patients suffering significant damage from osteoarthritis, such as those in need of knee replacement; or the many patients who are not good surgical candidates for knee replacement. This study will help select doses to establish safety, tolerability, and effectiveness in subsequent clinical trials.

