5.0 STUDY PURPOSE AND OBJECTIVES

The purpose of this study is to gather evidence for the safety, tolerability, and efficacy of XT-150 as a treatment for pain associated with OA.

- The primary objective of this study is to confirm the safety and tolerability of a single intra-articular dose of XT-150.
- The secondary objective is to establish the analgesic efficacy of a single intraarticular dose of XT-150 as a treatment for pain in participants with OA of the knee.

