10.8 Adverse Events of Special Interest

10.8.1 Localized Signs of Infection or Inflammation at the Injection Site

Events that, in the opinion of the Investigator, may represent localized signs of infection or inflammation at the XT-150 injection site (e.g., pain, erythema, swelling, pruritus, warmth, hematoma, induration) must be recorded as AEs on the CRF. In general, these events will be temporally related to the injection.

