13.4 Safety Analyses

All participants who receive any amount of study drug (Safety Population) will be included in the safety analyses.

Safety will be evaluated by presenting summaries of AEs and vital signs. Safety variables will be tabulated by treatment group.

Adverse events will be graded using the CTCAE v5.0 and will be coded using the Medical Dictionary of Regulatory Affairs (MedDRA®), Version 18 or higher. AEs will be collected for each participant from the signing of the informed consent through the last study visit on Day 360.

A treatment-emergent adverse event (TEAE) is defined as an AE that occurs during or after study drug administration. The incidence of TEAEs will be presented by system organ class (SOC) and preferred term (PT), by SOC, PT, and relationship to the study drug administration, and by SOC, PT, and severity. In addition, the incidence of serious TEAEs and TEAEs leading to discontinuation of study drug will be presented by SOC and PT.

Descriptive statistics for clinical laboratory test results, and vital signs, and for changes from Baseline, will be presented by time point. Baseline is defined as the measurement closest to, but prior to, the administration of study drug. Incidences of potentially clinically significant clinical laboratory results, and vital signs, as defined in the SAP, will also be summarized by time point. A summary of abnormal physical examination findings will also be presented.

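### Protocol 10.5.1 and 10.8.1 give opposing recording rules for the injected knee, so non-serious flares attributed to OA can be missing from the TEAE tables

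*Protocol*

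**What the plan says.** Safety comes first in this trial: "The primary objective of this study is to confirm the safety and tolerability of a single intra-articular dose of XT-150" (Protocol 5.0). Protocol 13.4 says how it is judged: "Safety will be evaluated by presenting summaries of AEs and vital signs". The product goes into the diseased joint: "Study drug will be administered by intra-articular (IA) injection into the joint space of the Index Knee" (Protocol synopsis).

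Two recording rules then apply to that joint.

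- Protocol 10.5.1: "Osteoarthritis-related events should not be considered or recorded as AEs unless the event fits the definition for an SAE".
- Protocol 10.8.1, on events of special interest: "Events that, in the opinion of the Investigator, may represent localized signs of infection or inflammation at the XT-150 injection site", with pain, swelling and warmth among the examples, "must be recorded as AEs on the CRF. In general, these events will be temporally related to the injection".

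Protocol 10.5.1 does not define which events count as osteoarthritis-related, does not separate the injected knee from other joints, and makes no exception for worsening after dosing. Neither section refers to the other.

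**The concern.** Knee pain or swelling after an intra-articular injection may be a local reaction, the underlying disease, or both. An investigator who calls it OA is told to leave it out of the AE record. One who thinks it may be a local reaction must enter it. Attribution is thus decided before recording, although the opening of 10.5.1 defines an AE without regard to cause and Table 5 in 10.6.1 already provides a later step for causality.

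Protocol 4.4.2 names injection-site reactions as the most common XT-150-related events. An unclear recording rule for the injected joint therefore affects the local tolerability result that the trial most needs to report.

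**Working it through.** No figure in the plan needs reproducing. The check is a reading of the passages, followed by a simple calculation for scale.

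**1. Can one event fall under both rules?** Take a non-serious episode of pain and swelling in the Index Knee.

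| Question | Protocol 10.5.1 | Protocol 10.8.1 |
|---|---|---|
| Trigger | Event is osteoarthritis-related | Investigator thinks it may be local infection or inflammation |
| Joint | Any, Index Knee not excepted | Injection site, i.e. the Index Knee |
| Instruction | Do not record unless an SAE | Record |
| Precedence stated | No | No |

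The triggers do not exclude each other, so the answer is yes.

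**2. Which events are most exposed?** Protocol 10.8.1 expects local events to be close in time to the injection. Protocol 4.1 says "low levels of human IL-10var protein are produced over the following weeks". A flare some weeks after dosing is compatible with the product's action, yet is easily put down to OA. A pain-only flare is exposed too, because it leaves no sign to examine.

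**3. What do the other data streams catch?**

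- *Physical examination (SAP 8.2).* Findings become AEs only if they meet the protocol's AE definition, which leads back to the exclusion.
- *Injection-site examination (SAP 8.2).* It is tabulated by arm and visit without depending on AE coding. It sees only signs present at the visit, and Protocol 6.2 allows a telephone contact for COVID-19 reasons, when no joint can be examined.
- *KOOS.* The symptom, activity-pain and function items look back one week. Stage A has 7 post-dose visits (Days 7, 30, 60, 90, 120, 150, 180). At nominal dates the recall windows cover 7 × 7 = 49 of 180 days, or 49/180 = 27%. The other 131 days fall outside them. By contrast, AEs are asked about since the last visit (Protocol 9.5, 9.6), so the AE record covers the whole interval.
- *Pain treatment.* Changes are recorded (Protocol 8.7.1, 9.5), but this shows a flare only indirectly, and only if treatment changed.

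**4. Scale, under assumed rates.** Let the true flare rates be p₀ on placebo and p₁ on one XT-150 dose, and let a share f in each arm be called OA and not recorded. The recorded difference is (1 − f)(p₁ − p₀). The recorded ratio is (1 − f)p₁ / (1 − f)p₀ = p₁/p₀, unchanged.

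With p₀ = 5%, p₁ = 15% and 90 per arm, the expected true counts are 90 × 0.05 = 4.5 and 90 × 0.15 = 13.5. The difference of 10 points becomes 7.5, 5 or 2.5 points for f = 25%, 50% or 75%.

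The next table gives the chance that a notional two-sided 5% comparison of 90 with 90 would show the difference: Φ{(Δ − 1.96·SE₀)/SE₁}, where Δ is the recorded difference and SE₀, SE₁ are the pooled and unpooled standard errors.

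| True rates | f = 0 | 25% | 50% | 75% |
|---|---|---|---|---|
| 5% vs 15% | 61% | 48% | 34% | 19% |
| 10% vs 20% | 47% | 36% | 25% | 14% |
| 10% vs 25% | 76% | 61% | 43% | 23% |

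The rates and f are assumptions with no source in the documents. The table shows only how quickly a visible imbalance fades.

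**The case against.** The strongest reply is that 10.8.1 is the specific rule and has a low threshold. The event need only possibly be local inflammation, and recording is then mandatory, whereas 10.5.1 is general and worded as a recommendation. On that reading 10.8.1 governs the injected knee and 10.5.1 covers background disease. Investigators are blinded and there is a placebo arm, so labelling should not differ by arm. Local reactions also have their own by-arm examination table, Protocol 13.4 adds a summary of abnormal physical findings, and KOOS is collected at every visit. Keeping symptoms of the studied disease out of the AE record while measuring them as efficacy is a common choice, and recording every fluctuation could bury true reactions.

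Much of this stands. It rules out the reading that Index Knee flares disappear from the safety evaluation: SAEs are always kept, suspected local reactions must be entered, and signs present at a visit reach the examination summary. It also rules out reading the power figures as a loss this trial would suffer. SAP 8.2 makes safety descriptive, so no AE test is planned, and flare rates are nowhere stated.

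Two things remain. The precedence of 10.8.1 is a sensible inference that the protocol does not state, so sites may differ. And even under that inference, a flare the investigator attributes wholly to OA stays out of the TEAE tables, and the other streams need not show it if it is pain-only or resolves between visits. The worry about burying true reactions is met by asking for a clear change from the participant's baseline.

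**Conclusion.** The two sections conflict for the injected knee and must be reconciled. If 10.5.1 is followed as written, non-serious Index Knee flares attributed to OA can be missing from the TEAE tables, and the remaining safeguards are partial.

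The size is unknown. It depends on how often flares occur and what share investigators attribute to OA. If the share lost is equal across arms, the absolute difference shrinks in proportion and the ratio does not change. Nothing in the documents suggests that the loss would favour one arm.

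The conclusion rests on the visible text. Some rows of the assessment schedules and the content of Protocol 9.4 on the period between visits are not shown and may add capture. They could not settle which recording rule prevails unless they addressed it directly. This is a correction worth making for a trial whose primary objective is safety; it does not invalidate the planned safety summaries.

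**What to change.** Amend 10.5.1 to say that the OA exclusion does not apply to the Index Knee after injection and that 10.8.1 takes precedence there. Events in that knee that are new, or clearly worse than the participant's baseline (pain, swelling, effusion, warmth, stiffness), are recorded as AEs whatever their attribution, and the relatedness field in Table 5 carries the causality judgment. Keep the exclusion for other joints. In the SAP, add a Stage A table of these events by arm beside the injection-site examination summary.

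The cost is a short protocol change, one table, and somewhat more AE entries, some overlapping with WOMAC pain. The concurrent placebo arm keeps the comparison fair.

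The SAP Addendum says its analyses were defined after database lock and unblinding, so a new recording rule can help only later studies. For this trial, the report can disclose the exclusion and show Index Knee examination findings and WOMAC pain worsening by arm next to the TEAE tables.
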